7.6. Treatment Compliance

The investigational product will be administered at the clinical site, and documentation of treatment administration will occur at the site.

Every attempt will be made to select patients who have the ability to understand and comply with instructions. Noncompliant patients may be discontinued from the study. The time and day of drug administration will be recorded. Drug accountability records will be maintained by the study site.

The specifications in this protocol for the timings of safety, PK, and GD sampling are given as targets, to be achieved within reasonable limits. Modifications may be made to the time points based upon the safety and PK information obtained. The scheduled time points may be subject to minor alterations; however, the actual time must be correctly recorded in the CRF. Failure to obtain samples due to clinical issues, such as problems with venous access, will not be considered a protocol violation, but written documentation will have to be provided to the sponsor for all missing samples (regardless of reasons) to facilitate data reconciliation before study completion.

Any major modifications that might affect the conduct of the study, patient safety, and/or data integrity will be detailed in a protocol amendment.

7.7. Concomitant Therapy

Patients will continue the basal insulin regimen established during the insulin transition period throughout the entire study except when presenting safety issues (see Section 7.4); in this case, the investigator will discuss a change of the regimen of basal insulin to prevent any medical problems. Any change in the basal insulin regimen will be captured in the patient diary and CRF.

Patients may continue their stable concomitant medication at the time of study entry at regular, unchanged doses during the study (for example, antihypertensive medication, lipid-lowering agent, thyroid hormone replacement medication, hormonal contraception or hormonal replacement therapy).

Drugs that are known inducers, or inhibitors of cytochrome P450 (CYP) 2C8 are specifically excluded. Additional drugs are to be avoided during the study unless required to treat an AE or for the treatment of an ongoing medical problem.

In general, the addition of new concomitant medication should be avoided; however, paracetamol (maximum 4g/24hours) may be administered at the discretion of the investigator for treatment of headaches etc. If the need for concomitant medication (other than paracetamol) arises, inclusion or continuation of the patient may be at the discretion of the investigator after consultation with a Lilly clinical pharmacologist or CRP. Any medication used during the course of the study must be documented.

Patients should not initiate new over-the-counter or prescription medication or nutritional supplements that affect blood glucose or the body's sensitivity to insulin or that promote weight loss 14 days before dosing or throughout the study.

Patients should not apply any creams or lotions to the abdominal skin on the morning of the injection or during the inpatient study procedure

7.8. Treatment after the End of the Study

Patients will continue their previous insulin regimen after the final study MMTT and associated procedures have been completed.

8. Discontinuation Criteria

Patients discontinuing from the study prematurely for any reason must complete adverse event and follow-up procedures per Schedule of Activities (Section 2) of this protocol.

8.1. Discontinuation from Study Treatment

Discontinuation of the investigational product for abnormal liver tests **should be considered** by the investigator when a patient meets 1 of the following conditions after consultation with the Lilly designated medical monitor:

- ALT (alanine aminotransferase) AST (aspartate aminotransferase) >8X for patients ULN (upper limit of normal)
- ALT or AST >5X ULN for patients sustained for more than 2 weeks or
- ALT or AST >3X ULN and total bilirubin level (TBL) >2X ULN or INR >1.5 or
- ALT or AST >3X ULN the appearance of fatigue, nausea, vomiting, right upper-quadrant pain or tenderness, fever, rash, and/or eosinophilia (>5%)
- ALP (alkaline phosphatase) >3X ULN
- ALP>2.5X ULN and TBL >2X ULN
- ALP>2.5 ULN with the appearance of fatigue, nausea, vomiting, right quadrant pain or tenderness, fever, rash, and/or eosinophilia (>5%).

8.1.1. Discontinuation of Inadvertently Enrolled Patients

If the Sponsor or investigator identifies a patient who did not meet enrollment criteria and was inadvertently enrolled, the patient must be discontinued from the study.

8.2. Discontinuation from the Study

Patients will be discontinued in the following circumstances:

- Enrollment in any other clinical study involving an investigational product or enrollment in any other type of medical research judged not to be scientifically or medically compatible with this study
- Participation in the study needs to be stopped for medical, safety, regulatory, or other reasons consistent with applicable laws, regulations, and good clinical practice (GCP)
- Investigator Decision
 - if the patient, for any reason, requires treatment with another therapeutic agent that has been demonstrated to be effective for treatment of the study indication, discontinuation from the study occurs prior to introduction of the new agent
 - Participation in the study needs to be stopped for safety reasons in the case of a severe hypo- or hyperglycaemic episode (see Section 9.5.6.3 and Section 9.5.6.2)
- Patient Decision
 - the patient requests to be withdrawn from the study.

Patients who discontinue the study early will have end-of-study procedures performed as shown in the Schedule of Activities (Section 2).

8.3. Patients Lost to Follow-up

A patient will be considered lost to follow-up if he or she repeatedly fails to return for scheduled visits and is unable to be contacted by the study site. Site personnel are expected to make diligent attempts to contact patients who fail to return for a scheduled visit or were otherwise unable to be followed up by the site.

9. Study Assessments and Procedures

Section 2 lists the Schedule of Activities, detailing the study procedures and their timing (including tolerance limits for timing).

Appendix 2 lists the laboratory tests that will be performed for this study.

Appendix 5 provides a summary of the maximum number and volume of invasive samples, for all sampling, during the study.

Unless otherwise stated in subsections below, all samples collected for specified laboratory tests will be destroyed within 60 days of receipt of confirmed test results. Certain samples may be retained for a longer period, if necessary, to comply with applicable laws, regulations, or laboratory certification standards.

Investigators must document their review of each laboratory safety report.

9.1. Efficacy Assessments

This section is not applicable for this study

9.2. Visit Description

9.2.1. Lead-In and Insulin Transition

After completing all screening procedures according to the Schedule of Activities (Section 2), patients will return to the CRU for the lead-in visit and receive instructions on the insulin transition. The lead-in site visit is to take place at least 2 weeks prior to Period 1, Day -2. At the lead-in site visit, patients will switch from their prescribed short-acting insulin to Humalog provided by the site. Patients will also transition from their current regimen of basal insulin to site-provided insulin glargine according to the following guidance:

- At least 2 weeks prior to CRU admission for Period 1, Day -2, patients will switch from either NPH insulin, insulin detemir or insulin glargine to using site-provided insulin glargine. The starting dose will be at the investigator's discretion using patient's current insulin regimen as reference.
- Adjustments may be made in consultation with site investigator following feedback obtained from the patient during at least twice-weekly telephone follow-up as part of the insulin-transition period.
- Once a stable dose has been established, patients will remain on it through to study completion

Additionally, at the lead-in site visit, patients will be provided with general diabetes training including, but not limited to: proper insulin-injection technique, dose calculation for short-acting insulins, correct self-monitoring of plasma glucose with a standardized glucometer, and interpretation of results, symptoms, and treatment of hypoglycemia. In addition to the study

insulin, the site will also provide the glucose meter, test strips, control solution, and lancets. A diary will also be provided as described in section 9.5.7.

9.2.2. Dose-Finding Assessment

After transitioning to a stable dose of insulin glargine, patients may return to the CRU on Period 1, Day -1 in the early morning for the dose-finding assessment, which may begin between 07:00 and 11:00. Patients may arrive at the CRU on the evening of Day -2 if necessary. Patients will have fasted for at least 10 hours prior to the test meal (see Section 6.3.1). The objective of the dose-finding assessment is to determine an appropriate, individualized insulin lispro dose of LY900014 or Humalog to be administered with the standardized liquid test meal during the Study MMTT (see Section 9.2.3.2). The patient's blood glucose will be measured to select a Humalog dose for the dose-finding assessment meal test as follows:

- if the patient's blood glucose is within the range of 70 to 180 mg/dL (3.9 to 10.0 mM), the patient will be given Humalog at the dose the patient would have taken at home
- the dose-finding meal test should not be carried out if the patient's blood glucose is not within the range of 70 to 180 mg/dL (3.9 to 10.0 mM) prior to start of the dose-finding meal test. The dose-finding meal test may be rescheduled as judged by the investigator (see Section 6.2.1)

Immediately (within 1 minute) after the Humalog dose has been selected and administered, the patient will receive a standardized liquid test meal consisting of two cans of 8 fl/oz Abbott Ensure Plus (approximately 100 g of carbohydrates total in test meal). Patients are expected to complete each test meal within 15 minutes of starting the meal.

The patient's blood glucose will be measured every 20 minutes for 5 hours postmeal to select a Humalog dose for the MMTT as follows:

- if the patient's blood glucose is within the range of 70 to 240 mg/dL (3.9 to 13.3 mM), for 5 hours postmeal, the selected Humalog dose will be used for the insulin lispro dose (LY900014 and Humalog) to be administered with the MMTTs but can still be adjusted if necessary based on the clinical judgement of the investigator
- if the patient's blood glucose is not within the range of 70 to 240 mg/dL (3.9 to 13.3 mM), the dose of Humalog will be adjusted based on the investigator's judgement or if the investigator is unable to make a decision regarding the Humalog dose after completing the initial test, the dose-finding assessment may be repeated once within 3 days of the initial assessment
- if, during the dose-finding assessment, the patients' blood glucose drops below pre-test baseline, the site investigator may make further adjustments of the insulin lispro dose

Following completion of procedures associated with the dose finding assessment, patients may be offered a meal. Patients will remain inpatient at the CRU until the Study MMTT for Period 1 Day 1 the following day.

9.2.3. Study Period CRU Visits

9.2.3.1. Run-In

Before the start of the run-in period, the cannulation of 2 veins will be performed. A variable IV infusion of glucose (20% dextrose solution) or insulin glulisine will be initiated in order to obtain a blood glucose target level of 135 ± 15 mg/dL (7.5 ± 0.8 mmol/L). Any insulin infusion should be tapered off and stopped 30 minutes prior to start of the test meal. For the last 30 minutes prior to trial product administration, the target blood glucose concentration should be targeted without any glucose infusion. If this target glucose range is not attained before 11:00 AM, the meal test will be halted and may be performed on a separate visit; each meal test can only be repeated once (see Section 6.2.1 for rescheduling)

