| Dose-finding | | | | X (Period 1 only) | | | Following insulin transition, patients will undergo dose-finding with Humalog and a test meal. To take place between 07:00 and 11:00. Blood glucose concentrations will be monitored every 20 minutes for 5 hours postmeal (see Section 9.2.2). See Section 6.2.1 for rescheduling. |

| Procedure | Sign Informed Consent | Screening | Lead-in | Study Period (Periods 1 to 4) | | Follow-up/Early discontinuation | Comments |
|------------------------------|-----------------------|-----------------|-------------------------|-------------------------------|---------------------------------------|---------------------------------|--|
| | | | | Day -1 | Day 1 | | |
| Randomization | | Days -30 to -17 | 14 days prior to Day -2 | X | | ≥ 14 days after discharge | To take place before run-in of Period 1 Day 1 |
| Pregnancy test | | X | | X | | X | Serum pregnancy test will be performed at screening and urine pregnancy tests will be performed at admission for Period 1 and at follow-up (see Appendix 2) |
| Standard dinner | | | | X | | | Approximately 19:00 |
| Medical Assessment | | | | X | Predose and before discharge from CRU | X | Medical assessment includes medical review and targeted examination, and as appropriate review of concomitant medication, patient diary and MMTT exclusion criteria (see Section 6.2.1) |
| Glucose stabilization/run-in | | | | | X | | From approximately 7 hours to 30 minutes before dosing: infusion of glucose (dextrose solution) or insulin glulisine to achieve a target blood glucose concentration of 135 ±15mg/dL (7.5 ±0.8 mmol/L). Blood glucose concentrations will be monitored at a minimum of 30-minute intervals (see Section 9.2.3.1 and 9.7.1.1). See Section 6.2.1 for rescheduling. |

| Procedure | Sign Informed Consent | Screening | Lead-in | Study Period (Periods 1 to 4) | | Follow-up and Early discontinuation | Comments |
|---|-----------------------|-----------------|-------------------------|-------------------------------|--|-------------------------------------|--|
| | | | | Day -1 | Day 1 | | |
| Blood glucose sampling (MMTT) | | Days -30 to -17 | 14 days prior to Day -2 | | -30, -15, 0 minutes pre-meal, 10, 20, 30, 40, 50, 60, 70, 80, 90, 100, 110, 120, 135, 150, 165, 180, 195, 210, 225, 240, 300 minutes post-meal | ≥ 14 days after discharge | 0-minute time point sample to be taken at the start of the meal. |

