5.4. Scientific Rationale for Study Design

The study is a 4-period crossover design to reduce the variability of insulin PK and GD, as each patient will act as his/her own control. The total number of patients needed with a crossover design is less than the number needed with a parallel group design. A maximum duration of approximately 6 weeks is allowed for patients to complete all 4 assigned periods to minimize the risk of insulin resistance/changes in mean glycemic control during the study.

Randomization and blinding are used to avoid bias introduced through an association between allocation order of investigational medicinal product (IMP) and patient characteristics. The Lilly clinical pharmacologist (CP)/Lilly study team will be unblinded.

In each study period patients will undergo a run-in period before the MMTT using a variable insulin and glucose IV infusion. This run-in period will allow for improved comparability of the postprandial glucose response to a mixed meal after treatment with LY900014 and Humalog administered either immediately before the start of the meal, or 20 minutes following the start of the test meal. This run-in aims to achieve similar preprandial glucose levels for all patients before the start of the test meal and thereby reduces the variability of the postprandial glucose response. Insulin glulisine has been chosen for the IV optimization of blood glucose during the run-in because insulin glulisine does not cross-react with the insulin lispro-specific assay used for the PK analysis.

Under this design, if two periods occur on consecutive days, the interval between the last bolus on the first day and the first bolus on the second day is much longer compared to the length of time that the treatment (LY900014 or Humalog) lasts in the bloodstream; therefore, no carryover effect is assumed. This enables PK and GD data from the breakfast meal tests of each period to be analyzed independently and separately.

A minimum of approximately 21 hours washout between the test meals allows for a complete washout of study drug administered with the MMTT and glucose response and prevents carry-over effects.

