9.2.3.2. Study MMTT

Each patient's individual, short-acting insulin (Humalog) may be administered before the start of a standard dinner (at approximately 19:00). If a correction dose of short-acting insulin needs to be administered after the meal, no more than 6 U of short-acting insulin (Humalog) should be administered between 7 and 12 hours before the scheduled intake of liquid test meal

The meal test may start in the early morning at approximately 08:00 with allowance up to 11:00, if required, to ensure the patient's blood glucose is stable and at target, with the premeal activities as specified in the Schedule of Activities (Section 2). LY900014 and Humalog will be administered at two different times: either immediately before the start of the meal or 20 minutes following the start of the test meal at each of the 4 periods according to the randomisation sequence. For each MMTT, the patient should stay in a semisupine position for 2 hours postdose. The patient will not be allowed to consume water for 2 hours after the MMTT assessment begins; however, water may be consumed freely 2 hours postmeal.

A standardized liquid test meal will be administered on Day 1 for each of the 4 treatment periods. Patients are expected to complete each test meal within 15 minutes of starting the meal. Patients will be without further food intake from the start of the meal to completion of blood collection (approximately 420 minutes) unless required to treat hypoglycemia (see Section 9.5.8).

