9.7.1.1. Glucose Samples (Run-In Period)

Blood glucose concentrations will be monitored at a minimum of 30-minute intervals during the run-in period on Day 1 (from approximately 7 hours before dosing).

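### The run-in's glucose-free window is tied to dosing while the baseline samples are tied to the meal, so in the +20-minute arms dextrose is permitted until 10 minutes before the meal; tie the window to the meal

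*Protocol*

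**What the plan says.** Protocol 9.2.3.1 uses two clocks in neighbouring sentences. Insulin follows the meal: "Any insulin infusion should be tapered off and stopped 30 minutes prior to start of the test meal". Glucose follows the dose: "For the last 30 minutes prior to trial product administration, the target blood glucose concentration should be targeted without any glucose infusion". The run-in row of the Schedule of Activities puts both infusions on the dosing clock: "From approximately 7 hours to 30 minutes before dosing: infusion of glucose (dextrose solution) or insulin glulisine". Section 9.7.1.1 starts run-in monitoring on that clock too: "during the run-in period on Day 1 (from approximately 7 hours before dosing".

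Glucose sampling in the meal test is on the meal clock, at -30, -15 and 0 minutes and onward, with the "0-minute time point sample to be taken at the start of the meal". Protocol 10.3.3.1 and SAP 9.4.1 average those three samples into the baseline that is subtracted in ΔAUC(0-2h) and ΔAUC(0-5h). Treatments A and C are dosed immediately before the meal, B and D 20 minutes after it starts.

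The stated purpose is premeal. Section 5.4 says: "This run-in aims to achieve similar preprandial glucose levels for all patients before the start of the test meal". Section 9.2.3.2 allows the start to slip to 11:00 so that "blood glucose is stable and at target, with the premeal activities as specified in the Schedule of Activities".

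**The concern.** The two clocks agree only when the dose is given at time 0. In the +20 arms, 30 minutes before dosing is 10 minutes before the meal, so dextrose may still be running when the -15 sample is taken. By the Schedule insulin may be running too, which contradicts 9.2.3.1. Neither document stops dextrose relative to the meal in those arms. Section 9.2.3.2 asks for stable glucose at target, which is not the same as infusion-free, and it refers back to the Schedule for the premeal activities.

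A premeal rule that differs by timing arm is confounded with the timing term in the glucodynamic (GD) model, and the crossover does not cancel it. No cross-timing contrast is named or powered, but the synopsis describes a study of meal-to-dose timing, so the two timings are likely to be compared.

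**Working it through.** **Plan's own figure.** Protocol 10.1 gives about 80% power for a -30 mg·h/dL difference in ΔAUC(0-2h), with 30 completers and an SD of within-patient difference of 56.20. A paired t-test (noncentral t, 29 df, two-sided 5%) gives 80.7%, so the figure reproduces. SE = 56.20/√30 = 10.26 mg·h/dL.

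**Timing.** Latest permitted dextrose, on the meal clock, is dose time minus 30.

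| Arms | Dextrose may run to | Minutes from stop to the -30, -15, 0 samples |
|---|---|---|
| A, C (dose at 0) | -30 | 0, 15, 30 |
| B, D (dose at +20) | 20 - 30 = -10 | -20, -5, +10 |

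The -15 sample can fall 5 minutes before the stop, and the 0 sample only 10 minutes after it. Dextrose is allowed up to -30 in every arm, so the infusion preceding the -30 sample does not differ by timing. Read literally, the +20 window runs from -10 to +20 and asks for 135 ± 15 mg/dL while the patient takes the test drink ("approximately 100 g of carbohydrates total in test meal", as described in 9.2.2).

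**Which contrasts move.** Add a constant s to both +20 arms in a balanced four-sequence crossover with patient and period effects. LY900014 minus Humalog changes by 0 at each timing, and so does the interaction. LY900014 +20 minus 0, Humalog +20 minus 0 and the timing main effect each change by s. A common shift also changes the LY900014/Humalog ratio at +20, because numerator and denominator move together.

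**Size (illustration only; the documents give no shift).** Let d be the shift in the -15 sample, r the fraction that persists after the meal and f the fraction of +20 periods with dextrose running after -30. The baseline of an exposed period moves d/3. In absolute size the mean ΔAUC(0-2h) moves f × 2d/3 × (1 - r), and ΔAUC(0-5h) moves f × 5d/3 × (1 - r). Rejection is for a truly null cross-timing contrast, assuming that SD 56.20 also holds for cross-timing differences.

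| d (mg/dL) | f | r | ΔAUC(0-2h) shift | Shift/SE | Rejection |
|---|---|---|---|---|---|
| 5 | 100% | 0 | 3.3 | 0.32 | 6.1% |
| 15 | 100% | 0 | 10 | 0.97 | 15.6% |
| 5 | 100% | 0.5 | 1.7 | 0.16 | 5.3% |
| 15 | 100% | 0.5 | 5 | 0.49 | 7.6% |
| 15 | 50% | 0 | 5 | 0.49 | 7.6% |
| 15 | 25% | 0 | 2.5 | 0.24 | 5.6% |
| 5 | 25% | 0 | 0.83 | 0.08 | 5.1% |

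At f = 100% and r = 0, ΔAUC(0-5h) moves 8.3 to 25 mg·h/dL.

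**Ratio at +20.** Assume a Humalog mean ΔAUC(0-2h) of 100 to 200 and a difference of -30. With mean 100 and a fall of 10 in both arms, 70/100 = 0.700 becomes 60/90 = 0.667. With mean 200 and a rise of 3.3 in both, 170/200 = 0.850 becomes 173.3/203.3 = 0.852. The range is 0.002 to 0.033.

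**Baseline covariate (separate; precision only).** With baseline SD b, adjustment removes a component of SD 2(1 - r) × b × √2 from the paired difference. For b = 5 and r = 0 this is 14.14, leaving √(56.20² - 14.14²) = 54.39 and power 83.1%. For b = 3 and r = 0.75, power is 80.7%. For b = 15/√3 = 8.66 (uniform over the whole ±15 band) and r = 0, it is 88.1%. Using 28 df instead of 29 costs at most 0.1 point. Within-patient residual df before the covariate are 120 - 30 - 3 - 3 = 84.

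**The case against.** The strongest reply is that no sensible site would follow the literal text. Nobody can hold 135 ± 15 mg/dL through a 100 g carbohydrate drink, and Sections 5.1, 5.4, 7.4.1 and 9.2.3.2 all tie the target to the start of the meal. That reading is probably right: the dosing anchor looks like a drafting slip written with time-0 dosing in mind. It makes the point minor. It does not remove the permission, which appears in two places, or the conflict between 9.2.3.1 and the Schedule, which different clinical research units could resolve differently.

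A reader might infer that the comparison of LY900014 with Humalog is biased. It is not. The rule is the same for both products at each timing, and SAP Section 8 admits GD data only as LY900014/Humalog pairs within a timing. The only powered GD contrast is at 0 minutes, and the primary PK endpoints do not use this baseline.

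A reader might also take 15.6% as the expected error rate. That needs dextrose after -30 in every +20 period, the largest assumed shift, always of one sign, and no persistence. Run-in uses glucose or insulin as needed, titrated to one target in all arms, so neither full exposure nor a consistent direction is implied. This part of the objection stands.

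Two smaller objections also stand. The 9.7.1.1 wording is immaterial, since 20 minutes lies within an approximate 7 hours. The covariate does not follow from the anchoring problem: ΔAUC is already baseline-subtracted, and the gain is small under moderate assumptions.

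**Conclusion.** The inconsistency is real and minor. In the +20 arms the protocol permits dextrose until 10 minutes before the meal, and the Schedule permits insulin until then against 9.2.3.1, while the baseline is sampled on the meal clock. The exposure is confined to 0 versus +20 contrasts, the timing main effect and the +20 Fieller ratios.

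The documents do not establish that any shift occurs, or its size or direction. Within the illustration, 3.3 to 10 mg·h/dL and 6.1% to 15.6% rejection are the upper bound, reached only with 100% exposure, a same-sign 5 to 15 mg/dL shift in the -15 sample alone and no persistence. With 25% to 50% of periods exposed and a 15 mg/dL shift, the mean shift is 2.5 to 5 mg·h/dL and rejection 5.6% to 7.6%. Every rejection figure borrows the SD of 56.20 for cross-timing differences. The case for the change rests on consistency and negligible cost, not on a demonstrated bias.

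**What to change.** **Main change.** In Protocol 9.2.3.1 keep the insulin sentence. Reword the next one to say that, in all four treatment-timing combinations, no glucose is infused during the 30 minutes before the test meal starts and the glucose target is to be met over that interval. In the run-in row of the Schedule of Activities, end the infusion window 30 minutes before the start of the test meal instead of before dosing. Moving 9.7.1.1 to the meal clock is optional tidying. Rescue treatment under 9.5.8 stays as written. Dextrose then stops by -30 in every arm and the two sections agree. The cost is one sentence and one phrase, with no new procedure or sample and no change to sample size or stated power.

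**Separate and optional.** In the SAP 9.4.2 text and code, add period-specific baseline glucose (the mean of -30, -15 and 0) and the patient's mean baseline to the GD model. Record this in SAP Section 11, which now reports no changes, or align Protocol 10.3.3.2 and the synopsis. Protocol 10.3 requires an amendment only if a principal feature changes. The data are already collected, and the cost is one of about 84 within-patient df and one between-patient df. Power for the -30 mg·h/dL difference goes from 80.7% to about 80.7-83% for an assumed baseline SD of 3 to 5 mg/dL, and to at most 88% if the SD is 8.66 with no persistence. This does not replace the main change.
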